8. OUTPUT PRESENTATIONS

Appendix 1 shows conventions for presentation of data in outputs.

The shells document provided with this SAP describe the presentations for this study and therefore the format and content of the summary tables, figures, and listings to be provided by IQVIA Biostatistics.

9. DISPOSITION AND WITHDRAWALS

All patients who provide informed consent will be accounted for in this study. Cenduit will be the primary source for the randomization information.

9.1. DISPOSITION

Patient disposition and withdrawals will be presented for the RND set using frequency counts and percentages by treatment. Patients who withdrew after week 24 (for 24-week stratum) and after week 48 (for 48-week stratum) will be included in the tables. Separate tables will be provided for patient disposition by treatment and by visit. The following patient sets will be presented per stratum and overall:

- Number of patients rescreened with approval
- Number of patients rescreened without approval
- Number of patients randomized
- Number of patients randomized and treated
- Number of patients who completed the full study, including follow-up visit
- Number of patients who completed treatment period in the study, up to Week 24 (overall, 24-week stratum and 48-week stratum)
- Number of patients who completed treatment period on study medication (overall, 24-

week stratum and 48-week stratum)

- Number of patients who discontinued the study medication (overall, 24-week stratum and 48-week stratum)
- Primary reason for early study medication discontinuation
- Number of patients who withdrew from the study (overall, 24-week stratum and 48-week stratum)
- Primary reason for early study withdrawal

Study medication and study discontinuation/completion of patients will be presented by the date of the “End of Treatment/Disposition” page of the eCRF. The date of study discontinuation/completion will be last available date within eCRF and the date of study medication completion will be identified from End of Treatment page of the eCRF.

The number of study discontinuation and study medication discontinuation before 24 weeks visit (all subjects) and before 48 weeks (48-week stratum only) will be summarized by treatment group and analyzed and presented through Kaplan-Meier plot using log-rank test, as described in Section **Error! Reference source not found.** of the SAP.

Time to study medication discontinuation by subgroups of actual background medication strata and actual smoking strata will be presented through Kaplan-Meier plot.

Reasons for exclusion from each analysis set, as well as patients not meeting eligibility and randomization criteria will be presented for the ENR set with patients classified according to the randomized treatment. Patients not randomized will be presented in a separate category.

9.1.1. DERIVATIONS

Study day of early study medication discontinuation = Last day of study medication intake - First day of study medication intake + 1.

Study day of early study discontinuation = Last day in the study - First day of study medication intake + 1.

Visit for discontinuation will be presented using six subgroups (Not treated, \geq day 1 and \leq week 6, $>$ week 6 and \leq week 12, $>$ week 12 and \leq week 24, $>$ week 24 and \leq week 36, $>$ week 36 and \leq week 48), using the corresponding visit day windowing:

- week 6 = study day 53

- week 12 = study day 95
- week 24 = study day 179
- week 36 = study day 263
- week 48 = study day 336

9.2. PROTOCOL DEVIATIONS

PDs will be defined in the BDR report and the list will be finalized before the DBL. Identified PDs that affect the BDR and analysis populations will be finalized before DBL.

9.3. EVALUATION INCLUDING EXCLUDED SITES

Sites [REDACTED] were removed from the Randomized set. As a check of this exclusion, the patient disposition will be performed in the Extended Randomized set.

10. DEMOGRAPHIC AND OTHER BASELINE CHARACTERISTICS

Demographic data and other baseline characteristics will be presented for the RND. If there is a difference in patients between RND and mITT population, then demographic data and other baseline characteristics will also be presented for mITT.

Demographic data and other baseline characteristics will also be presented by subgroups of actual background medication strata and actual smoking strata for mITT.

No statistical testing is planned be carried out for demographic or other baseline characteristics. The following demographic and other baseline characteristics will be reported for this study:

- Age (years)
- Age-class (years) (<65, ≥65)
- Gender at birth
- Ethnicity (Hispanic or Latino, Not Hispanic or Latino (subgroup for rest of categories), Not Reported)
- Race
- Country
- Weight (kg)
- Height (cm)
- BMI (kg/m²)

[REDACTED]	[REDACTED]	[REDACTED]	[REDACTED]
[REDACTED]	[REDACTED]	[REDACTED]	[REDACTED]
[REDACTED]	[REDACTED]	[REDACTED]	[REDACTED]
[REDACTED]	[REDACTED]	[REDACTED]	[REDACTED]

- FEV₁ reversibility at screening (yes, no)
- Modified Medical Research Council (mMRC) questionnaire score
- Pre- and post-bronchodilator FEV₁ (both in liters and in percentage of predicted normal)
- Post-bronchodilator FEV₁/forced vital capacity (FVC)
- Time since initial diagnosis of COPD (years)
- Background medication strata [yes (subgroup for yes: LAMA, LAMA/ICS, LABA, LABA/ICS), no] –actual
- Known to have Chronic Bronchitis (yes, no)
- Known to have Emphysema (yes, no)
- Smoking strata (current, former) –actual recorded in the eCRF
- Number of cigarettes per day, Number of years smoking, Number of Pack Years
- COPD severity based on post-bronchodilator FEV₁ (Mild, Moderate, Severe, Very severe)

10.1. DERIVATIONS

- BMI (kg/ m²) = weight (kg)/ height (m)²
- Time since initial diagnosis of COPD = (date of consent – date first diagnosed)/365.25
- Pack Years = Number of packs per day x number of years smoking

Reversibility status is calculated based on pre-bronchodilator and post-bronchodilator FEV₁ values taken at Screening. If patient has increase of $\geq 12\%$ and $\geq 200\text{mL}$ then patient is reversible, else patient is non-reversible.

Age (years) collected in the eCRF will be used for the analysis.

Pack Years is automatically calculated in the eCRF and this value will be used in the summaries. COPD severity will be derived as follows based on post-bronchodilator screening spirometry:

- Mild: post-bronchodilator FEV₁ $\geq 80\%$ predicted
- Moderate: $50\% \leq$ post-bronchodilator FEV₁ $< 80\%$ predicted
- Severe: $30\% \leq$ post-bronchodilator FEV₁ $< 50\%$ predicted
- Very severe: post-bronchodilator FEV₁ $< 30\%$ predicted
-

10.2. EVALUATION INCLUDING EXCLUDED SITES

As a check of the exclusion of sites [REDACTED] from the mITT, the demography and baseline disease characteristics will be performed in the mITT Extended.

-

11. SURGICAL AND MEDICAL HISTORY

Surgical and Medical History information will be presented for the SAF set.

- Surgical History will be coded using the Medical Dictionary for Regulatory Activities (MedDRA) central coding dictionary. The version of MedDRA to be used will be specified prior to database lock. Data captured on the “Surgical Procedure History” page of the eCRF will be presented by System Organ Class (SOC) and Preferred Term (PT) for each treatment group.
- Medical History will be coded using MedDRA central coding dictionary. The version of MedDRA to be used will be specified prior to database lock.
 - Medical History conditions, captured on the “Medical History” page of the eCRF, are defined as those conditions which stop prior to or at Screening visit and will be presented by SOC and PT for each treatment group.

12. CONCOMITANT ILLNESSES

Concomitant Illnesses will be presented for the SAF set.

- Concomitant Illnesses will be coded using MedDRA central coding dictionary. The version of MedDRA to be used will be specified prior to database lock.
 - Concomitant Illnesses, captured on the “Medical History” page of the eCRF, are conditions which started prior to the first treatment dose and are ongoing at the date of first treatment dose, and will be presented by SOC and PT for each treatment group.

13. MEDICATIONS

Prior, prior concomitant and concomitant medications will be presented separately for the SAF set and coded using the World Health Organization (WHO) drug code and summarized by Anatomical Therapeutic Clinical Classification System (ATC) levels 1, 2 and 4.

Possible therapeutic subgroups include ICS, LABA, LAMA, corticosteroids, short-acting B2 agonist, short-acting anti-muscarinic and combinations specified below, which are defined in a separate spreadsheet provided by the medical data reviewer. Combinations to be analyzed:

1. Oral or intravenous (IV) Corticosteroids
2. Oral or IV Corticosteroid & Other combinations
3. LAMA
4. LAMA/LABA

5. LAMA & OTHER COMBINATIONS
6. LABA
7. LABA & Other combinations
8. ICS/LAMA/LABA or ICS/LABA/LAMA
9. ICS/LAMA
10. ICS/LABA
11. ICS & Other Combinations
12. SABA/Short-Acting Anti-Muscarinic
13. SABA
14. SABA & other combinations
15. SABA/ICS
16. SABA/ Corticosteroid
17. Short-Acting Anti-Muscarinic

See Appendix 2 for handling of partial dates for medications, in the case where it is not possible to define a medication as prior, concomitant, or post treatment, the medication will be classified by the worst case; i.e. concomitant.

- ‘Prior’ medications are medications which started prior to the first dose of study medication and stopped prior to the first dose of study medication.
- ‘Prior Concomitant’ medications are medications which started prior to the first dose of study medication and ended on or after the date of first dose of study medication or were ongoing at the end of the study.
- ‘Concomitant’ medications are medications which:
 - started on or after the first dose of study medication and started no later than last day of study medication intake,
 - AND ended on or after the date of first dose of study medication or were ongoing at the end of the study.
- ‘Post’ medications are medications which started from the day after the last dose of study medication.

Prior, prior concomitant and concomitant COPD medications will be presented separately for the SAF set. COPD medications are those provided by medical review and will be presented as preferred term and ATC levels 1, 2 and 4.

Data captured on the “Concomitant Medications” page of the eCRF will be presented for each treatment group. Patients with multiple medications within an ATC/ therapeutic subgroup will only be counted once for that level.

[REDACTED]	[REDACTED]	[REDACTED]	[REDACTED]
[REDACTED]	[REDACTED]	[REDACTED]	[REDACTED]
[REDACTED]	[REDACTED]	[REDACTED]	[REDACTED]
[REDACTED]	[REDACTED]	[REDACTED]	[REDACTED]

Oxygen therapy and CPAP will be listed separately to other medications. Oxygen therapy is defined by ATC code: “V03AN” and route is not Oral; CPAP is defined by ATC code: “R07AX” and route is not Oral.

14. STUDY MEDICATION EXPOSURE

Exposure to study medication in days will be presented for the SAF set.

The dates of first dose of study medication administration will be taken from the “Drug Exposure” page of the eCRF (Day 1). The date of last dose of study medication administration will be taken as the latest date among all from the “Drug Exposure” and “Drug Exposure – Evening Blinded Study Medication Clinic Dosing” pages of the eCRF. If no drug exposure were made at last visit and the dispensed drug supply was insufficient to cover use up to last visit, the last exposure day will be set to the day the drug supply should have been empty if patient had been compliant to twice daily regimen. Interruptions and compliance are not taken into account for duration of exposure.

Study medication exposure will be presented using summary statistics by total number of days, and using frequency counts by subgroups: 1-42 days, 43-84 days, 85-126 days, 127-168 days, 169-210 days, 211-252 days, 253-294 days, 295-336 days, and >336 days.

14.1. DERIVATIONS

Duration of exposure (days) = date of last study medication administration – date of first study medication administration + 1.

15. COMPLIANCE

Compliance to study medication based on dispensed and returned unused ampules and secondarily based on e-Diary entries will be presented for the SAF set.

Compliance will be presented for 24-week and 48-week strata separately using summary statistics by time intervals (Day 1 to Week 12, Weeks 12-24, Weeks 24-48, and full study length), as well as using frequency counts by subgroups: <50%, 50-70%, 70-80%, 80-90%, 90-100% and >100%.

15.1. STUDY MEDICATION COMPLIANCE

Study medication compliance will be summarized by treatment group in 2 ways:

- The number of ampules dispensed and unused returned will be taken from “Drug

[REDACTED]	[REDACTED]	[REDACTED]	[REDACTED]
[REDACTED]	[REDACTED]	[REDACTED]	[REDACTED]
[REDACTED]	[REDACTED]	[REDACTED]	[REDACTED]
[REDACTED]	[REDACTED]	[REDACTED]	[REDACTED]

Accountability” page of the eCRF.

- Drug intake as recorded in the e-diary.

Patient is non-compliant, for study medication intake collected through the number of ampules dispensed/returned, if identified as taking less than or equal to 70% of blinded study medication during the period Day 1 to Week 12, or less than or equal to 50% over the study (Day 1 to Week 24 for the 24-week stratum, Day 1 to Week 48 for the 48-week stratum). Calculations will not include time after treatment withdrawal.

15.1.1. DERIVATIONS

Compliance with study medication will be calculated on the number of ampules count (total dispensed – total returned) divided by the prescribed number of ampules expressed as a percentage, see calculations below.

Patient should take the study medication twice daily and record it in their e-Diary apart from Week 24 visit when patient’s last dose will be in the morning.

Patients are dispensed ampules at Visit X and return at Visit Y, however in the eCRF returned ampules will be recorded under Visit X.

- For time interval compliance to study medication will be calculated as follows:

$$\frac{([N \text{ of Ampules dispensed at Visit X}] - [N \text{ of Ampules returned at Visit Y}])}{\text{Denominator1}} * 100$$

Where Denominator1 is calculated with the following rules:

- N_1 = Number of ampules expected calculated based on total N of Ampules dispensed, taking into account 2 ampules per day, apart from last dose date for completed patients where we would only consider 1 ampule per day.
- For non-Week 24 (for the 24-week stratum) or non-Week 48 (for the 48-week stratum) (last week) return ampules visit: N_2 = Number of ampules between dispensing and returning visit calculated: $\{[Date \text{ of Visit Y}] - [Date \text{ of Dispensing at Visit X}] + 1\} * 2$.
- For Week 24 (for the 24-week stratum) or Week 48 (for the 48-week stratum) (last week) return ampules visit: N_2 = Number of ampules between dispensing and returning visit calculated: $\{ \{ [Date \text{ of Visit Y}] - [Date \text{ of Dispensing at Visit X}] + 1 \} * 2 \} - 1$.
- If $N_1 \geq N_2$ then Denominator1 = N_2 .
- If $N_1 < N_2$ then Denominator1 = N_1 .

-
- Overall Compliance to study medication will be calculated as follows:

$$\frac{(\text{N of Ampules total dispensed} - \text{N of Ampules total returned})}{\text{Denominator2}} * 100$$

Where Denominator2 is calculated with the following rules:

- N_1 = Number of days calculated based on total N of Ampules dispensed, taking into account 2 ampules per day, apart from last dose date for completed patients where we would only consider 1 ampule per day.
- N_2 = Number of days between dispensing and returning visit calculated: $\{ \{ [\text{Date of Visit } X(n)] - [\text{Date of Dispensing at Visit } 1] + 1 \} * 2 \} - 1$.
- If $N_1 \geq N_2$ then Denominator2 = N_2 .
- If $N_1 < N_2$ then Denominator2 = N_1 .

For patients who permanently discontinue the study medication, the “Date of Visit X(n)”/ “Date of Visit Y” will be replaced by the last dose date of study medication, as specified in Section 14 of the SAP. Whereas for patients who completed study, the “Date of Visit X(n)”/ “Date of Visit Y” will be replaced by date of last dose.

Drug intake as recorded in the e-diary: percent of ‘yes’ responses. The denominator is the number of records for which the patient provided an answer (Yes or No) to drug intake questions (morning and evening) in the e-diary.

For time interval study medication e-diary compliance, use week’s windowing conventions described in Section 6.4 of the SAP. For Week 24 (for the 24-week stratum), use study day assigned to determine the date for weeks required or the time intervals, Week 12 and Week 24. The compliance will be calculated as follows:

$$\frac{(\text{Week } X^* < \text{number of 'yes' responses entered in the eDiary} \leq \text{Week } Y)}{(\text{Week } X^* < \text{number of non - missing responses entered in the e - Diary} \leq \text{Week } Y)} * 100$$

*If Week X = Day 1, update “<” to be “≤”. For the 24-week stratum, if Week Y is Week 24 and patient has completed treatment then the last entry we expect is in the morning. Patient should not log any entries from and including evening of Week 24.

Similarly for Week 48 visit for the 48-week stratum, determine the time intervals using study day as described above for Week 12, Week 24, and Week 48. As above, if Week Y is Week 48 and patient has completed treatment the last entry expected will be morning and no further log entry

[REDACTED]

should be done including the evening of Week 48.

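### The SAP's overall compliance formula words its denominator in days under a numerator in ampules; followed as written, a fully compliant completer would score about 160–199% instead of 100%

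*SAP*

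**What the plan says.** SAP 15.1.1 opens by defining compliance as ampules dispensed minus ampules returned, "divided by the prescribed number of ampules expressed as a percentage". Two formulas follow.

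- **Time-interval formula.** N_1 is the "Number of ampules expected calculated based on total N of Ampules dispensed", at two per day. N_2 is also a number of ampules. The smaller is the denominator.
- **Overall formula.** The numerator starts from "N of Ampules total dispensed" and subtracts the total returned. N_1 is now the "Number of days calculated based on total N of Ampules dispensed", again at two per day. N_2 is introduced as the "Number of days between dispensing and returning visit calculated", but its expression multiplies the days by two and subtracts one. Again the smaller is taken: if N_1 is below N_2, "then Denominator2 = N_1".

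For both completers and discontinuers, the end date in N_2 is replaced by the date of last dose.

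SAP 15.1 sets two limits for flagging a patient as non-compliant on ampule counts. The early limit is "less than or equal to 70% of blinded study medication during the period Day 1 to Week 12". The alternative limit, which covers each stratum's full treatment length, reads "or less than or equal to 50% over the study". SAP 15 also reports full-study compliance in frequency bands, the highest being above 100%.

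**The concern.** The overall formula divides a count of ampules by the smaller of two quantities in different units. N_2 has an explicit expression, so its ampule count is clear whatever its label. N_1 has only words, and those words describe days of supply. With two ampules a day, days of supply is about half the ampule count, so the minimum rule will nearly always select it for a completer.

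The SAP is the programming specification. Two programmers could reasonably code N_1 differently and obtain full-study compliance values that differ about two-fold. Under the literal version, adherent completers would crowd into the band above 100%, patients who missed many doses would look adherent, and the 50% limit would act at a much lower true level than stated. Non-compliance is also among the possible reasons for exclusion from the per-protocol population (SAP 5.7).

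**Working it through.** The plan gives no worked compliance figure, so there is none to reproduce. The check applies the overall formula to a completer who takes every dose.

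**Inputs**
- One ampule per dose (Protocol 6.2, Table 5), twice daily, with only the morning dose on the final day (SAP 15.1.1).
- Nominal Week 24 is Day 169 and nominal Week 48 is Day 337 (SAP 6.4).
- Total ampules dispensed, D, is not stated. It is assumed to run from no surplus to a 25% surplus: 337 to 421 in the 24-week stratum.

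**Formulas**
- N_2 = (169 − 1 + 1) × 2 − 1 = 337 ampules, which is also the number of prescribed doses. For 48 weeks, N_2 = 337 × 2 − 1 = 673.
- N_1 as worded, for a completer = (D − 1)/2 + 1 days.
- Score = 337 / min(N_1, N_2).
- Share of prescribed doses at which the score equals 50% = 0.5 × min(N_1, N_2) / 337.

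**24-week completer who takes all 337 doses, literal reading**

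| Assumed surplus | D | N_1 (days) | Score | 50% limit reached at |
|---|---|---|---|---|
| 0% | 337 | 169 | 337/169 = 199% | 84.5/337 = 25% of doses |
| 5% | 354 | 177.5 | 190% | 26% |
| 10% | 371 | 186 | 181% | 28% |
| 20% | 404 | 202.5 | 166% | 30% |
| 25% | 421 | 211 | 337/211 = 160% | 105.5/337 = 31% of doses |

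The 48-week stratum behaves alike: 673/337 = 200% with no surplus and 673/421 = 160% with D = 841 (25% surplus).

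A 24-week completer who took half the doses (168.5) would score 168.5/169 = 100% with no surplus and 168.5/211 = 80% with a 25% surplus. The true value, 50%, is exactly at the limit.

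**Where the literal rule gives the right answer.** N_2 becomes the smaller once (D − 1)/2 + 1 exceeds 337, that is, D above 673, about double the need. It can also be the smaller for someone who stops soon after a dispensing. For example, with 84 ampules dispensed (assumed) and last dose on Day 21, N_1 = 84/2 = 42 and N_2 = 21 × 2 − 1 = 41. The denominator is then 41, and a patient who took every dose scores 100%. If the same patient stopped on Day 40, N_2 = 79, N_1 = 42, and the score would be 79/42 = 188%.

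**With N_1 in ampules.** The denominator is min(D, 337) = 337 at any surplus. Full compliance scores 100%, and the 50% limit falls at 168.5 ampules, half the prescribed doses.

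**The case against.** The best defence is that days is a slip for ampules. The opening sentence of SAP 15.1.1, the numerator, the parallel interval formula and N_2's own expression all point that way. It can also be said that the literal reading is selective: it ignores the label on N_2 while enforcing it on N_1. This is probably right about intent. It does not make the text safe, because N_1 has no expression to override its wording. Nor does taking both labels at face value help: N_2 would be 169 days under an ampule numerator, again giving 337/169 = 199%.

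Other parts of the defence stand and limit the point:

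- The non-compliance flag has two limbs. The Day 1 to Week 12 limb uses the interval formula, which is consistent.
- The per-protocol population is built around lung function at Week 12, the period that the unaffected limb covers. SAP 5.7 says only that reasons may include non-compliance, to be settled at blinded data review. It does not make the full-study 50% value a trigger for exclusion.
- A literal program would probably be noticed, because most adherent completers would land above 100%.

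**Conclusion.** The written derivation of overall compliance is wrong in its units and should be corrected. Followed literally, and assuming a 0–25% supply surplus, it gives a fully compliant 24-week completer about 160–199% and moves the full-study limit from 50% to about 25–31% of prescribed doses. What would be wrong is the reported full-study compliance, its frequency bands and the full-study limb of the flag.

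A reader might infer more than the documents support:

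- **A single inflation figure, such as 187%.** That needs about 360 ampules dispensed over 24 weeks, and neither kit size nor total supply is given. Only a range under a stated assumption is supportable.
- **That every value is inflated.** Patients for whom N_2 is the smaller, including some early discontinuers, score correctly.
- **That the 50% limit is inoperative.** It would still catch patients at or below about 25–31% of doses.
- **That efficacy conclusions are at risk.** The primary analysis is on the mITT population and does not use compliance. The per-protocol analysis is a sensitivity analysis, with little exposure to this limb.

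**What to change.** In the overall formula of SAP 15.1.1, define both quantities as numbers of ampules, as in the interval formula:

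- N_1 = ampules expected from the total dispensed.
- N_2 = {(date of last dose − date of first dispensing + 1) × 2} − 1.

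The minimum rule can stay. The cost is a change of label in two places, made before the compliance tables are programmed or, if they already exist, a check of which reading the program uses. No new data are needed.

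A separate point for the same edit: Protocol 9.4.3 sets full-study non-compliance at below 70%, while SAP 15.1 uses 50% or less, and SAP 3.3 does not list the change. The two should be reconciled or the change recorded.

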5.7. PER-PROTOCOL POPULATION

The per-protocol (PP) population will contain all patients in the mITT who did not discontinue the study medication before study day 74 and did not experience any major/important PDs considered to have an impact on efficacy assessments involving lung function at week 12. Reasons for exclusion will be specified at a BDR meeting prior to DBL and may include violations of inclusion/exclusion criteria, violations of withdrawal criteria, incorrect randomization, use of prohibited medication, did not follow blinding procedures and non-compliance. Patients will be classified according to randomized treatment. If protocol deviations in terms of dosing errors are detected post unblinding, these will lead to exclusion only if patient has received and used the opposite study drug compared to what was specified in the randomization and that this use occurred prior to week 12.

Patients who were excluded from PP due to the study medication being discontinued before study day 74 are not considered as protocol violations.

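### The by-interval compliance formula moves the return-visit date to the date of last dose without limiting this to the final interval, so the Day 1 to Week 12 divisor is no longer doses due

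*SAP*

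**What the plan says.** SAP 15.1.1 describes ampule compliance as the count used "divided by the prescribed number of ampules expressed as a percentage". In the by-interval formula the numerator is ampules dispensed at Visit X minus ampules returned at Visit Y. The denominator, Denominator1, is the smaller of two counts:

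- N_1: "Number of ampules expected calculated based on total N of Ampules dispensed, taking into account 2 ampules per day".
- N_2: "Number of ampules between dispensing and returning visit calculated" as (Date of Visit Y − date of dispensing at Visit X + 1) × 2. One ampule is subtracted when the return visit is the last one (Week 24 or Week 48, by stratum). Other return visits have their own branch without the subtraction.

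When N_1 is the smaller, the rule reads "then Denominator1 = N_1".

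A later paragraph of the same section changes the dates. For patients who permanently stop study medication, the closing visit date "will be replaced by the last dose date of study medication, as specified in Section 14 of the SAP". For the rest: "Whereas for patients who completed study, the “Date of Visit X(n)”/ “Date of Visit Y” will be replaced by date of last dose". Neither sentence names an interval.

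SAP 15.1 flags a patient as non-compliant for taking "less than or equal to 70% of blinded study medication during the period Day 1 to Week 12". SAP 5.7 lists among possible reasons for exclusion from the per-protocol population "did not follow blinding procedures and non-compliance".

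**The concern.** Date of Visit Y occurs only in the by-interval formula, where it is the date on which that interval's supply comes back. Replacing it with the date of last dose is sensible for the last interval, because it stops the clock when dosing stops. In any earlier interval it does the opposite: it stretches a 6- or 12-week interval to the end of treatment. N_2 then stops measuring doses due and is too large to be the smaller of the two counts, so N_1 takes over. A patient who returns unused spares is scored as if those ampules had been missed.

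The two parts of SAP 15.1.1 therefore give different denominators for the same quantity. The Day 1 to Week 12 value carries the 70% limit, and non-compliance can lead to removal from the per-protocol set. That set supports sensitivity analyses of the primary endpoint (SAP 16.1.4) and the key secondary endpoints (SAP 16.2.4).

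**Working it through.** The plan states no compliance figure to reproduce, so the check evaluates its formula under both date rules.

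**Inputs**
- Formula and minimum rule: SAP 15.1.1. Limit of 70%: SAP 15.1.
- Nominal days from the weekly windows in SAP 6.4: Week 6 = Day 43, Week 12 = Day 85, Week 24 = Day 169, Week 48 = Day 337.
- Ampules dispensed from Day 1 to Week 12, called D: **not given**. Protocol 6.2.1 says only that kits are dispensed on schedule. Assumed range 170 to 240. The middle value of 208 = 2 supplies × (42 + 10) days × 2 ampules would cover the ±10-day visit window in SAP 6.4.

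**Step 1: actual return-visit date.** N_2 = (85 − 1 + 1) × 2 = 170. For any D of at least 170 the denominator is 170. Full use scores 170/170 = 100%, and the flag fires only at true compliance of 70% or less.

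**Step 2: date of last dose, as literally written.** Week 12 is not the last return visit, so the branch without the subtraction applies.
- 24-week stratum: N_2 = (169 − 1 + 1) × 2 = 338.
- 48-week stratum: N_2 = (337 − 1 + 1) × 2 = 674.

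**Step 3: the resulting denominator.** With N_1 taken as the interval's own supply, the smaller count is D throughout the assumed range, in both strata. Full use scores 170/D. A patient with true compliance c is flagged when c × 170/D ≤ 0.70, that is, when c ≤ 0.70 × D/170.

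| D (assumed) | Score at full use | Flag fires at true compliance of |
|---|---|---|
| 170 | 100% | 70.0% or less |
| 190 | 89.5% | 78.2% or less |
| 208 | 81.7% | 85.6% or less |
| 224 | 75.9% | 92.2% or less |
| 240 | 70.8% | 98.8% or less |

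Full use would itself be flagged from D = 243 (170/243 = 69.96%).

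**Step 4: supply by supply.** Drug is also dispensed at Week 6, and the SAP does not say how the two supplies combine into Day 1 to Week 12.
- Day 1 to Week 6: due (43 − 1 + 1) × 2 = 86; literal N_2 is 338 or 674.
- Week 6 to Week 12: due (85 − 43 + 1) × 2 = 86; literal N_2 is (169 − 43 + 1) × 2 = 254 or (337 − 43 + 1) × 2 = 590.

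With 104 ampules per supply, full use scores 86/104 = 82.7% in each, so the result does not depend on how they are combined.

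**Patients who stop drug.** The same stretching affects any interval that closed before the one in which they stopped.

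**The case against.** The best defence is that the section's own wording shows a final-interval intent. The divisor is described as the prescribed number, N_2 is tied to the returning visit, and there is a separate branch for return visits other than the last. On the literal rule that branch would never use its own visit date for a completer. The replacement sentence pairs Date of Visit Y with Date of Visit X(n), the closing date of the overall formula. SAP 15.1 excludes time after treatment withdrawal, and Protocol 6.6 assesses compliance from visit to visit. A careful programmer would probably apply the replacement to the last interval only. This stands as evidence of intent, but it does not supply the missing restriction.

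The dependence on supply size also stands: with D = 170 and N_1 read per interval, nothing is distorted.

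Two stronger readings are tempting, and the documents do not support them:

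- *Every completer is flagged.* Because N_1 refers to total ampules dispensed, a reader might take it over the whole study. Full use would then score 170/338 = 50.3% or 170/674 = 25.2%. But the numerator is the supply dispensed at Visit X less its returns. Dividing one interval's use by the whole study's supply is not a plausible meaning. The unclear wording of N_1 is a reason to define it, not to adopt this result.
- *Compliant patients will be dropped from the per-protocol set.* SAP 5.7 makes non-compliance a possible reason, settled at a blinded data review before database lock; falling below the limit does not exclude anyone automatically. Diary-based compliance is calculated separately without this replacement, so a large discrepancy could be noticed.

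**Conclusion.** The rule is wrong as written, with low to moderate severity. The unrestricted replacement contradicts the definition of N_2 in the same section. Applied literally, it changes the Day 1 to Week 12 divisor from doses due to ampules dispensed. The size rests on an assumed supply: none if dispensed equals due, about 18 percentage points at 208 ampules for a fully compliant patient (100% − 81.7%), and about 29 points at 240 (100% − 70.8%).

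The text does not show that the programmed values would be wrong, since the intended rule is probably the sensible one. The effect is confined to the interval compliance table, the non-compliance flag and, through blinded review, possible per-protocol exclusions. The primary analysis uses the mITT population and does not depend on compliance, so it is unaffected.

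**What to change.** Replace the two unrestricted sentences in SAP 15.1.1 with wording such as: *For the interval containing the last dose, Date of Visit Y is replaced by the date of last dose; for earlier intervals the actual return-visit date is used.* Apply it both to completers and to patients who stop study medication. State that N_1 in Denominator1 is the ampules dispensed in that interval, and say how the Day 1 and Week 6 supplies combine into the Day 1 to Week 12 value.

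The cost is a few lines of SAP text and a check of the derivation program. No new data are needed. It should be settled before the blinded data review decides per-protocol membership.
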